6.3 Exploratory Efficacy Endpoints and Analyses

The exploratory endpoints are:

- Clinical diagnostic and laboratory assessments of renal structure and function (including eGFR, serum creatinine, and proteinuria) to assess changes in the rate of progression of renal disease.
 - Clinical diagnostic assessments of renal structure and function consist of results from renal ultrasounds (cortical thickness, length, and volume by treated/untreated kidney) and renal scintigraphy (differential renal function by treated/untreated kidney).
 - Laboratory assessments considered exploratory endpoints include: eGFR as estimated by the 2009 CKD-EPI serum creatinine equation, serum creatinine, 24 hour urine albumin, and 24 hour urine protein.
- Patient-reported outcomes from the Kidney Disease Quality of Life (KDQOL) and EQ-5D-5L surveys obtained at baseline (i.e., before REACT injection) through 24 months after the last REACT injection.
- Time to dialysis

6.3.1 Quality of Life (QoL)

An exploratory analysis will be conducted to examine potential changes in health-related Quality of Life (HR-QoL). Subjects will complete the KDQOL-SFTTM survey (i.e., Kidney Disease and Quality of Life Short Form) and EQ-5D-5L survey at baseline and through 24 months after the last REACT injection.

The KDQOL-SF is a 36-item, validated, HR-QoL instrument relevant to patients with kidney disease. ^[4] This disease-specific, HR-QoL instrument consists of the following subscales:

- The “SF-12 measure of physical (PCS) and mental (MCS) functioning” contains items about general health, activity limits, ability to accomplish desired tasks, depression and anxiety, energy level, and social activities.
- The “Burden of Kidney Disease subscale” contains items about how kidney disease

interferes with daily life, takes up time, causes frustration, or makes the respondent feel like a burden.

- The “Symptoms and Problems subscale” contains items about how bothered a respondent feels by sore muscles, chest pain, cramps, itchy or dry skin, shortness of breath, faintness/dizziness, lack of appetite, feeling washed out or drained, numbness in the hands or feet, nausea, or problems with dialysis access.
- The “Effects of Kidney Disease on Daily Life subscale” contains items about how bothered the respondent feels by fluid limits, diet restrictions, ability to work around the house or travel, feeling dependent on doctors and other medical staff, stress or worries, sex life, and personal appearance.

The subscales for burden of kidney disease, symptoms and problems, and effects of kidney disease, as well as the composite scores for PCS and MCS will be calculated as described in the reference [4].

The EQ-5D-5L is a five-item, validated, HR-QoL instrument [5]. EQ-5D-5L health states can be summarized by a single summary number (index value) which reflects how good or bad a health state is according to the preferences of the general population of a country/region.

The actual and change from baseline in KDQOL scores and EQ-5D-5L index values at each time point post REACT injection will be summarized descriptively using the IAS.

Measurements taken after dialysis has started will be removed from all efficacy analyses. Listings of QOL assessments will be provided for the FAS and will include a notation for assessments taken after the start of dialysis so that it is clear which records are included in the efficacy analyses.

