### **4.5. Study Duration**

Subjects will begin their series of REACT injection(s) as soon as the autologous REACT preparation is made available. Assuming a one-month interval prior to the first REACT injection, and assuming a 6-month interval before the second injection, plus a 24-month follow-up period after the final injection, the study duration would be:

- 31 months for a series of 2 REACT injections

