## 5. STUDY POPULATION

### 5.1. Subject Inclusion Criteria

Unless otherwise noted, subjects must satisfy each inclusion criterion to participate in the study. Inclusion criteria will be assessed at the Screening Visit, prior to renal biopsy, and before each REACT injection unless otherwise specified.

1. The subject is male or female, 30 to 65 years of age on the date of informed consent.
2. The subject has an established diagnosis of T2DM.
3. The subject has an established diagnosis of diabetic nephropathy as the underlying cause of renal disease.
4. The subject has an established diagnosis of CKD not requiring renal dialysis, defined as having an eGFR between 14 and 20 mL/min/1.73m^2 inclusive at the Screening Visit and prior to REACT injection.
5. The subject has blood pressure less than 150/90 at the Screening Visit, prior to renal biopsy, and prior to REACT injection(s). At the time of the biopsy and injections, the subject's BP should not be significantly below the previously recorded stable pressure.
6. The subject has stable blood pressure and is maintained on a stable anti-hypertensive medication regimen, if treatment for hypertension is necessary. If treatment includes an angiotensin-converting-enzyme inhibitor (ACEI) or an angiotensin receptor blocker (ARB), that treatment must have been initiated at least 8 weeks prior to renal biopsy. Treatment must be stable during the 6-week period immediately prior to REACT injection. Stable treatment is defined as dose adjustment to no less than one half of the current dosage or to no more than 2 times the current dosage. Dose interruptions up to 7 days due to medical necessity are allowed.
7. A minimum of 3 measurements of eGFR or sCr should be obtained at least 3 months apart prior to the Screening Visit or within the previous 24 months to define the rate of progression of CKD. The subject should have adequate, historical clinical data to provide a reasonable estimate of the rate of progression of CKD. The Medical Monitor may be consulted to ensure there is sufficient data.
8. The subject is willing and able to refrain from NSAID consumption (including aspirin) as well as clopidogrel, prasugrel, or other platelet inhibitors during the period beginning 7 days before through 7 days after both the renal biopsy and REACT injection(s).

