4.5 Handling of Dropouts or Missing Data

Missing data will remain missing. No imputation of missing data will be performed.

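### Quality-of-life scores obtained after dialysis start are left out of the by-visit summaries, so late means describe only subjects still off dialysis

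*SAP*

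**What the plan says.** SAP 6.3.1 has subjects complete the KDQOL and EQ-5D-5L "at baseline and through 24 months after the last REACT injection". Actual values and changes from baseline at each time point "will be summarized descriptively using the IAS", the set of subjects with at least one injection. The section then adds: "Measurements taken after dialysis has started will be removed from all efficacy analyses". Later records appear only in a listing, with a flag. The same rule stands in SAP 6.2 (renal laboratory values), 6.3.2 (ultrasound) and 6.3.3 (scintigraphy).

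SAP 4.5 states: "Missing data will remain missing. No imputation of missing data will be performed". No reason for the removal is given, and no second quality-of-life summary is planned. Protocol sections 9.4 to 9.7 contain no such exclusion, and SAP section 10, which lists departures from the protocol, does not mention it.

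Dialysis is reported elsewhere. SAP 6.3.5 gives the number and percentage starting dialysis with Kaplan-Meier quartiles and a plot, and SAP 6.3.4 marks dialysis start on the individual subject plots.

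**The concern.** For creatinine-based eGFR and serum creatinine the rule has a sound reason: once dialysis starts, the values no longer reflect native kidney function. That reason does not carry over to a questionnaire. The SAP calls both instruments validated, describes the KDQOL as relevant to patients with kidney disease, and includes "problems with dialysis access" in its symptom subscale. A score given on dialysis is a real observation of how the subject is doing.

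Whether a score is removed depends on the outcome. Protocol section 2 gives delay of renal replacement therapy as the aim of treatment. A subject who starts dialysis has reached the event that the product is meant to delay, and from then on leaves every quality-of-life mean. With nothing imputed, each late mean is conditional on being alive, in follow-up and dialysis-free, but the table does not say so. A reader would take it as the experience of the treated group.

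**Working it through.** **Plan's own figure.** There is none to reproduce. The documents give no dialysis rate, slope, effect size or power.

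**Inputs from the documents**
- Entry: "an eGFR between 14 and 20" mL/min/1.73 m², not on dialysis (Protocol 5.1, criterion 4).
- Duration: "31 months for a series of 2 REACT injections" (Protocol 4.5). Less the one-month lead-in, this is 31 - 1 = 30 months from first injection, or 6 months to the second injection plus 24 after it.
- Sample size: up to 10 (SAP 9).

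**Assumptions, not in the documents**
- Baseline eGFR B is uniform on 14 to 20.
- Each subject declines linearly with slope S, normal with mean -2 to -5 per year and SD 2.5.
- Dialysis starts when eGFR falls to a threshold c of 7 to 9.

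**Step 1: how many leave the table.** At t years eGFR is B + S·t, and a subject is on dialysis if B + S·t ≤ c. For scale, a subject entering at 17 who loses 4 per year reaches 17 - 4 × 2.5 = 7 at 30 months.

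**Step 2: effect on the eGFR mean.** Compare the mean change in those remaining with the mean when each dialysed subject is held at c. The gap is the first minus the second. Simulated results at the four corners of the range:

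| Mean slope per year | c | On dialysis, 18 mo | Gap, 18 mo | On dialysis, 30 mo | Change in those remaining, 30 mo | Dialysed held at c, 30 mo | Gap, 30 mo |
|---|---|---|---|---|---|---|---|
| -2 | 7 | 5% | 0.3 | 22% | -2.7 | -4.2 | 1.5 |
| -2 | 9 | 11% | 0.5 | 32% | -1.8 | -3.6 | 1.8 |
| -5 | 7 | 27% | 0.9 | 65% | -6.1 | -8.5 | 2.3 |
| -5 | 9 | 45% | 1.0 | 76% | -4.8 | -7.1 | 2.3 |

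Over this range 5-45% are on dialysis at 18 months and 22-76% at 30 months. The gap is 0.3-1.0 and 1.5-2.3 mL/min/1.73 m² respectively. Of 10 treated subjects, 10 × (1 - 0.22) = 7.8 down to 10 × (1 - 0.76) = 2.4 would still contribute at the last visit, before any other loss.

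**Step 3: chance that the rule bites at all.** With per-subject dialysis probability p, the chance that at least 1 of 10 is affected is 1 - (1 - p)^10. For p = 0.2 this is 1 - 0.8^10 = 0.89. For p = 0.4 it is 1 - 0.6^10 = 0.99.

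**Step 4: quality of life.** Let p be the proportion on dialysis, and let m_off and m_on be the mean changes off and on dialysis. The planned table reports m_off. The mean over all collected scores is (1 - p)·m_off + p·m_on. The difference is p·(m_off - m_on). With p between 0.22 and 0.76 at 30 months, each point by which subjects on dialysis fare worse moves the reported mean by 0.22 to 0.76 points. The documents give no value for m_on, so this shows how the rule works and does not estimate the bias.

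**The case against.** The strongest reply is that dialysis is not hidden. SAP 6.3.5 counts it in the same analysis set and adds a Kaplan-Meier plot. SAP 6.3.4 marks it on each subject's plot, the flagged listings keep every record, and SAP section 4 prints the non-missing n. For laboratory values, SAP 7.3 also gives a by-visit summary with no stated dialysis exclusion. With at most 10 subjects, a careful reader can work out who left. All of this stands, and it defeats any inference that the plan discards the data or leaves dialysis unrepresented. It does not supply a quality-of-life summary that includes subjects on dialysis, and no by-visit efficacy table separates dialysis from death, withdrawal or a missed visit.

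A reader might also infer that mean eGFR will look stable because failures drop out. The working does not support that: those remaining still lose 1.8 to 6.1 at 30 months, so the decline is attenuated but visible. At 18 months the gap is small.

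The dialysis-access item cuts both ways. Subjects must be off dialysis at entry, so the item has no natural baseline, and change in that subscale is not fully like for like. That calls for a note, and is no reason to drop the other subscales or the EQ-5D-5L.

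Finally, these endpoints are secondary or exploratory, the primary endpoint is safety, and no hypothesis is tested. That limits the importance of the point.

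**Conclusion.** The concern holds for quality of life. As written, the plan drops usable KDQOL and EQ-5D-5L scores from the summaries because of a poor renal outcome, so the late means describe dialysis-free subjects only. They probably look more favourable than the whole treated group. That direction assumes that subjects on dialysis report worse quality of life, which the documents do not establish.

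The share removed at the last visit, 22-76%, rests on the assumed slopes, spread and dialysis threshold. If nobody starts dialysis the rule has no effect. For eGFR and creatinine the exclusion is defensible, and the gap of 1.5-2.3 mL/min/1.73 m² at 30 months (0.3-1.0 at 18 months) only illustrates the selection. The fault there is one of labelling: the tables do not say why n falls or that the means are conditional. The change should be made, but nothing in the primary safety analysis depends on it.

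**What to change.** - **SAP 6.3.1:** summarise all collected KDQOL and EQ-5D-5L scores in the injection analysis set regardless of dialysis. Keep the pre-dialysis-only table as supportive. Note that the dialysis-access item has no like-for-like baseline.
- **SAP 6.2 and 6.3.1 tables:** at each visit print the number on dialysis and the number dead beside n. Label the off-dialysis means as conditional on being dialysis-free.
- **Not advised:** ranking dialysis as the worst value across the SAP 6.2 laboratory panel. Several of those analytes, such as potassium and calcium, have no single worst direction. Where more than half have started dialysis, the median would only repeat what SAP 6.3.5 already shows.

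The cost is SAP wording and a few extra rows. No new data are needed, since the scores are already planned for collection and listing. The quality-of-life changes may look less favourable.

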6.3.2 Renal Ultrasound

The actual and change from baseline values for the renal ultrasound measurements of cortical thickness, length, and volume for the treated and untreated kidney will be summarized descriptively at each time point post REACT injection using the IAS.

Measurements taken after dialysis has started will be removed from all efficacy analyses. All renal ultrasound measurements will be presented in a data listing for the FAS. The listing will include a notation for assessments taken after the start of dialysis so that it is clear which records are included in the efficacy analyses.

6.3.3 Renal Scintigraphy

The actual and change from baseline values for the differential renal function results for the treated and untreated kidney renal scintigraphy results will be summarized descriptively at each time point post REACT injection using the IAS.

Measurements taken after dialysis has started will be removed from all efficacy analyses. A listing of all renal scintigraphy assessments will be provided for the FAS and will include a notation for assessments taken after the start of dialysis so that it is clear which records are included in the efficacy analyses.

6.3.4 Rate of Progression of Renal Disease

Using the IAS, the rate of progression of renal disease will be assessed graphically for eGFR as estimated by the 2009 CKD-EPI serum creatinine equation, serum creatinine, and 24 hour urine albumin, and 24 hour urine protein. For each subject a plot of the lab result versus time (in study days) will be displayed, showing vertical lines at biopsy date, 1st and 2nd injection, and the initiation of dialysis, if it is administered. Additionally, for eGFR, the rate of progression of renal disease will be assessed by estimating the annualized eGFR slope over time for each subject. Each subject will serve as his or her own control. The subject's previous medical history, which must include a minimum of 6 months of observation of renal function, will serve as the control for rate of progression of renal insufficiency. The historical eGFR measurements as well as all on study measurements taken prior to the first REACT injection will constitute the pre-injection period for this analysis.

The annualized rate of eGFR decline for the pre-injection, post-second injection, and post-injection periods will be estimated separately by linear mixed effects models. That is, separate models will be fit for each of the specific time periods: pre-injection, post-second injection, and post-injection periods. Each subject with a minimum of 3 observations during the period of interest will be modeled. The model will include unscheduled visits, and only the last measurement if there was a re-test on the same day.

For the pre-injection period, the linear mixed effects model will include eGFR as the dependent variable, and time (in years, derived as study day/365) as the independent variable. To account for between-subject variability in eGFR trajectories, random slopes and intercepts will be included. An unstructured covariance matrix will be used for the model. If the model cannot be fit with the unstructured covariance matrix, the following structure will be tried in the order listed below (decreasing number of parameters) until the one of them fit the model:

1. First-order autoregressive moving average (ARMA(1,1))
2. First-order autoregressive (AR(1))
3. Compound symmetry (CS)
4. Variance Components (VC)

For the post-secondary period, and separately for the post-injection period as a whole, linear mixed effects models will be fit including eGFR as the dependent variable, time (in years, derived as study day/365) as the independent variable, and baseline eGFR as a covariate. To account for between-subject variability in eGFR trajectories, random slopes and intercepts will be included. An unstructured covariance matrix will be used for the model. If the model cannot be fit with the unstructured covariance matrix, the same procedure as for the pre-injection period will be followed.

A table will be presented to display the following for each time period of interest: number of subjects included in the model, the estimated slope for the time variable, and the associated standard error. If no model can be fit, the table will simply display a message "Model did not converge."

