## 6. STUDY VISITS

The schedules of clinical assessments and procedures to be performed during the study are displayed in the time and events tables, i.e., [Table 1](#). Similarly, the schedules of sample collection and clinical laboratory evaluations planned for the study are displayed in the laboratory time and events tables, i.e., [Table 2](#). Before conducting any study specific assessments or procedures (including screening), the subject must provide written informed consent in accordance with ICH GCP guidelines and 21 CFR Part 50.

Due to the COVID-19 pandemic that began in March 2020, subject follow-up visits may be conducted remotely or via home health services to ensure the safety of the subject. Any procedures listed in the schedule of events that are not completed due to COVID-19 pandemic restrictions will be documented as protocol deviations. Clinical laboratory evaluations are permitted to be completed by a local lab convenient for the subject. Results of all evaluations performed by local laboratories will be collected by ProKidney.

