### 7.3.1. eGFR

GFR will be estimated using the Chronic Kidney Disease Epidemiology Collaboration (CKD-EPI) equation that incorporates both serum creatinine and Cystatin C. The specific assay for measuring creatinine will be defined by ProKidney, and the samples will be analyzed by the central laboratory. For comparison to each subject's historical values, it may be necessary to perform a second analysis at the site laboratory used to generate the historical data. The need for any additional assays conducted locally by the site laboratory will be defined at the Site Initiation Visit.

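### The pre-injection eGFR slope joins site-laboratory history to late, by default central-laboratory values with no laboratory term, so a shared laboratory offset would enter the control slope

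*SAP*

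**What the plan says.** SAP 6.3.4 compares each subject's eGFR decline after injection with his or her own earlier decline. The control period is defined thus: "The historical eGFR measurements as well as all on study measurements taken prior to the first REACT injection will constitute the pre-injection period". For that period, "the linear mixed effects model will include eGFR as the dependent variable, and time (in years, derived as study day/365) as the independent variable". Random intercepts and slopes are added, but no term for the laboratory. The post-second-injection and post-injection models have the same form, with time "and baseline eGFR as a covariate".

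On the source of the values, Protocol 7.3.1 says of study creatinine that "the samples will be analyzed by the central laboratory". For comparison with history it adds that "it may be necessary to perform a second analysis at the site laboratory used to generate the historical data", and leaves the need for such local assays to the Site Initiation Visit. Protocol section 6, in its COVID-19 paragraph, says: "Clinical laboratory evaluations are permitted to be completed by a local lab convenient for the subject". It continues: "Results of all evaluations performed by local laboratories will be collected by ProKidney".

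On the amount of history, Protocol 5.1 (criterion 7) says: "A minimum of 3 measurements of eGFR or sCr should be obtained at least 3 months apart prior to the Screening Visit". SAP 6.3.4 requires at least 6 months of observation, and Protocol section 2 refers to data from the 24 months before screening.

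When a test is repeated on one day, SAP 6.3.4 keeps only the final result. It does not say whether a site re-assay of a study sample counts as such a repeat. SAP section 10, which lists departures from the protocol, does not mention laboratory source.

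**The concern.** Historical values come before screening. On-study pre-injection values run from screening to the first injection, which is planned for about a month after biopsy. The default change from site to central laboratory therefore happens once, late in the control period, and laboratory is strongly correlated with time. In a model with time alone, a step at the end of the series is read as decline or improvement.

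The study has no concurrent control, and Protocol section 2 proposes that treatment will reduce the eGFR slope, so the pre/post slope comparison is the planned evidence for that proposal. If the central laboratory reads lower than the sites, the control slope is too steep and the comparison favours the product. If it reads higher, a benefit is hidden. The standard error would not reveal either, and enrolling more subjects would not remove an offset that they share.

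The protocol foresees the comparability problem by allowing a second local assay, but the SAP has no rule for the paired results. If the same-day rule is applied to them, whether the site or the central value stays in the model could depend on the order of entry.

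**Working it through.** The documents state no slope, offset or power for this analysis, so there is no planned figure to reproduce. The check is the effect of a 1-unit step on a fitted line.

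**Formula.** With n_h historical values and n_c central values, the least-squares slope of a 0/1 laboratory indicator on time is

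tilt = [n_h·n_c/(n_h + n_c)] × (mean t_c − mean t_h) / Sxx,

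where Sxx is the sum of squared deviations of all times from their mean. This is the bias in mL/min/1.73m² per year for each +1 unit of central-minus-local offset.

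**Inputs.** From the documents: at least 3 historical values at least 3 months apart, hence 6 months or more; screening up to 60 days before biopsy; a pre-biopsy visit 1–3 days before biopsy; injection about one month after biopsy; a pre-injection visit 10–14 days before injection. Assumed: central values at days −75, −32 and −12 (mean −39.7); 3 equally spaced historical values ending at day −90. The first factor is then 3×3/6 = 1.5.

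| History | mean t_h (days) | mean t_c − mean t_h (years) | Sxx | Tilt |
|---|---|---|---|---|
| 6 months | −181.25 | 0.388 | 0.366 | 1.5×0.388/0.366 = 1.59 |
| 12 months | −272.5 | 0.638 | 1.126 | 1.5×0.638/1.126 = 0.85 |
| 24 months | −455 | 1.138 | 3.958 | 1.5×1.138/3.958 = 0.43 |

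Four central values (days −76, −40, −12 and 0) give 1.60, 0.89 and 0.46. Ending the history at day −120 with the three central values gives 1.49, 0.83 and 0.43. Hence about 1.4–1.6, 0.8–0.9 and 0.4–0.5. A gap of 5.5 months between history and injection lowers the 6-month figure to about 1.3.

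**Mixed-model check.** Simulated with 10 subjects and 60 runs per scenario, under an assumed true slope of −4 per year, between-subject slope SD of 1.5 and residual SD of 1.2. Some fits gave convergence warnings, so this is a rough check. With 12 months of history, offsets of −1 and +1 gave mean slopes of −4.87 and −3.18. With 24 months and 5 values they gave −4.42 and −3.53. Size and direction agree with the table.

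**Follow-up.** If every value is central, a constant offset goes into the intercept and the tilt is 0. If some visits are local, it need not be. For the post-second-injection period, take days 14 and 28 and months 2, 3, 6, 9, 12, 15, 18, 21 and 24 (30.4 days per month), with the last two visits local. The factor is 9×2/11 = 1.636, the local mean is 684.0 days and the central mean 224.2. The difference, central minus local, is −459.8 days = −1.260 years, and Sxx = 4.95. The tilt is 1.636×(−1.260)/4.95 = −0.42. Other patterns, per +1 unit:

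| Local visits | Post-injection | Post-second injection |
|---|---|---|
| Last 2 | −0.28 | −0.42 |
| Last 4 | −0.47 | −0.63 |
| First 4 | +0.31 | +0.57 |
| Three mid-period | below 0.1 | below 0.1 |

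**Offsets that differ by subject.** If offsets were independent with mean 0 and SD 1 (assumed), the expected bias in the mean slope is about 0. Its SD is tilt/√10: 1.59/3.16 = 0.50, 0.85/3.16 = 0.27 and 0.43/3.16 = 0.14 for 6, 12 and 24 months.

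**The case against.** The strongest counter-case has four parts.

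- **Size.** The per-unit figures assume a common offset. With up to 10 subjects at up to 10 centres, site laboratories may differ in the sign and size of their offsets, and the bias in the mean slope would then partly cancel. One unit is already 5–7% of an eGFR of 14–20 (1/20 to 1/14). With 24 months of history the tilt is at the low end. This stands as a limit on magnitude. It does not show that no common offset exists.
- **Stakes.** The analysis is exploratory, no hypothesis test is planned, and SAP 6.3.4 tabulates the number of subjects, slope and standard error by period without a formal difference. Individual plots are also planned, where a large step might be seen, although laboratory source is not marked. This stands and limits the severity.
- **Sources.** A reader might infer that every early value is local, every late value central, and that the SAP discards the site re-assays. The documents do not go that far. Protocol 7.3.1 allows parallel site assays. Protocol 5.4 admits patients biopsied under RMCL-002, whose earlier laboratory is not stated. Read literally, the SAP's definition of the pre-injection period could include re-assays. What can be shown is that the SAP gives no rule for them.
- **Remedy.** A single local/central fixed effect is not a clean cure. In simulation it brought the mean slope back to about −4.0 when the offset was common. When offsets varied by subject it did not reduce the slope error (empirical SD 0.68 to 0.82 with 12 months of history, 0.49 to 0.50 with 24). With no offset but true late acceleration, it moved the 12-month slope from −4.99 to −4.61. It cannot be estimated in an all-central model. This stands, and it makes the single-laboratory fit the better main request.

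**Conclusion.** The point holds in a limited form. As written, the plan lets a systematic laboratory offset shared by subjects pass into the control slope, at about 1.4–1.6, 0.8–0.9 or 0.4–0.5 mL/min/1.73m² per year per unit for 6, 12 or 24 months of history. These figures rest on the assumed visit times and on a common offset. The offset itself is not in the documents, so the actual bias and its direction are unknown.

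Two stronger readings are not supported. One is that only the control slope can be affected: Protocol section 6 permits local laboratories and SAP 6.3.4 neither excludes nor marks such values, so the post-injection slopes can tilt too. The other is that the comparison is biased in favour of the product: the sign could go either way. No error rate or sample size depends on this analysis. I rate it minor to moderate.

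**What to change.** 1. Record the laboratory source of every eGFR value, historical and on-study.
2. State in SAP 6.3.4 that a paired site re-assay under Protocol 7.3.1 is not a re-test for the same-day rule, and say which value enters which fit.
3. Beside the planned fit, report a sensitivity fit of the pre-injection slope on site-laboratory values only: history plus site re-assays of on-study samples where they exist. Add matching central-only fits for the post-injection and post-second-injection slopes.
4. A laboratory fixed effect may be shown as a further sensitivity fit, with the caveat that it removes only a common offset and can absorb true late decline.

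No new visits are needed, but the source of historical values must be obtainable. The cost is precision. If only history remains, a single subject's least-squares standard error grows by √(Sxx of all values / Sxx of history). With the three central values and a 3-month gap between history and injection, that is √(0.366/0.125) = 1.71 for 6 months, √(1.126/0.5) = 1.50 for 12 and √(3.958/2) = 1.41 for 24. Over the other schedules tried with that gap, the increase is about 35–90%. It is larger with a longer gap, and smaller the more on-study samples have a site re-assay. For the optional fixed effect, the simulated model standard error rose from about 0.55 to 0.67 (12 months, 3 values) and from 0.47 to 0.52 (24 months, 5 values).
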